6.6.2 Determination of Sample Size

This is a pilot study therefore the appropriate sample size was estimated based on previous and current studies that achieved significance and involved this population and a similar approach to vitamin D supplementation.

We requested approval to enroll twice the number required, or 120 subjects, in order to overcome the potential for a higher than expected attrition (30%), or a particularly high level of enthusiasm for the study from beneficiaries and civilians working in the hospital.

Estimate Required Sample Size	60
Estimate Participant Drop Out / Withdrawal	30%
Total Enrollment Requirement	Minimum of 78, requesting 120

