metabolism in 97.5% of the population.²⁰ While debate surrounds a sufficient range for 25(OH)D, there does seem to be a general acceptance that the optimum range is between 30 – 60 ng/mL.⁵⁻⁷ The human body uses sunlight as the primary source of vitamin D and produces large quantities efficiently with limited UVB exposure.¹²⁻¹⁵ Therefore, a rational way to determine the optimum vitamin D range is by studying natural cutaneous vitamin D synthesis. It has been demonstrated that a single session of full body exposure to solar radiation can produce a time-released equivalent of approximately 10,000 IU of oral vitamin D.¹⁶ A safe upper limit for vitamin D is related to oral intake only. Cutaneous vitamin D production is automatically regulated by a photochemical reaction and pigmentation, preventing toxicity.¹⁷⁻¹⁹ Consequently, hypervitaminosis D is not possible when the only vitamin D source is skin production following exposure to UVB light. For all these reasons, an innovative alternative to address low vitamin D status in adults, Warfighters included, is needed.

5 Study Objectives

The specific aims for this project were:

1. Determine acceptability and feasibility of a standing phototherapy kiosk designed as a self-care intervention for AD and retired service members, beneficiaries, and DA civilians;
2. Demonstrate that narrow spectrum UVB delivered by the SPK is at least equivalent to D3 oral intake to raise or maintain serum 25(OH)D levels over a 10-week intervention period;
3. Examine the relationship of demographic variables, including gender, age, body mass index, body fat, ethnicity, and sun exposure to serum 25(OH)D levels in both groups.

6 Investigational Plan

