6.1 Overall Study Design and Plan

This non-inferiority study used a prospective, longitudinal, randomized design with repeated measures to address vitamin D sufficiency in AD, retiree, beneficiary, and DA civilian populations. It is important and necessary to conduct this study with adult humans, military personnel in particular, to determine acceptability and feasibility of this phototherapy kiosk as an addition to existing Warfighter resources to promote health and resilience. Following Madigan Army Medical Center (MAMC) Institutional Review Board Human Subjects and Ethics approval, the SPK will be installed in a location approved by the Radiation Safety Officer, the study team will be hired, and recruitment will begin for an anticipated 12-month project period. Approximately 120 volunteers will be approached from MAMC and Joint Base Lewis-McChord (JBLM), a large joint base in the Pacific Northwest, where over 25,000 Soldiers and Airmen train every day and regional beneficiaries' number ~98,000. Recruiting efforts will attempt to capture a representative sample of the population including both genders, diverse ethnicities, and a range of age (18-70 years) and body mass index (BMI), who have no contraindication for UVB exposure or oral vitamin D supplementation. In addition to walk-in volunteers, the research team will attend the JBLM Newcomer's Orientation. Using a computer-generated block design, volunteers will be randomized to one of two groups by the research pharmacist; 1) oral vitamin D supplementation, or 2) standing phototherapy kiosk with UVB exposure, for a 10-week period.

Comparison Group (CG) – Supplement

A MAMC research pharmacist will dispense a 70-day supply of the vitamin D3 600 IU oral supplement to subjects assigned to this group. The Project Director will work with the pharmacist to coordinate pick-up of supplement bottles for subjects or optimal in-person dispensing times.

Treatment Group (TG) – Phototherapy

The Project Director provides oversight for the phototherapy treatment. The kiosk will deliver the UVB dose under supervised conditions over a 1 – 10 minute interval based on the Fitzpatrick skin type with the subject wearing minimal or no clothing, preferably no more than a bathing suit, and protective eye-wear. The experience in the SPK was designed to be comfortable and user-friendly.

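### The required size of 60 rests on earlier studies having reached significance, which does not support it as adequate for showing the kiosk is at least equivalent to oral D3

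*Combined protocol and SAP*

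**What the plan says.** Section 6.6.2 opens by invoking pilot status and then says "the appropriate sample size was estimated based on previous and current studies that achieved significance". It describes these studies further only as sharing the population and using a comparable supplementation approach. It does not name them or give their designs, sizes or effects. Its table lists an estimated required size of 60, 30% dropout, and a total enrolment of "Minimum of 78, requesting 120". The text adds: "We requested approval to enroll twice the number required, or 120 subjects", which fixes 60 as the total over both arms.

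The question to be answered is set elsewhere. Section 6.1 states: "This non-inferiority study used a prospective, longitudinal, randomized design with repeated measures". Aim 2 in section 5 is to demonstrate that narrow-spectrum UVB from the kiosk "is at least equivalent to D3 oral intake to raise or maintain serum 25(OH)D levels over a 10-week intervention period". Section 6.5.3 makes serum 25(OH)D the primary endpoint for establishing this, and expects kiosk levels to match or not fall below those on supplement, with no number attached.

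On analysis, section 6.1 plans repeated measures ANOVA adjusted for covariates such as baseline 25(OH)D. Section 6.6.1 describes exploratory analyses with medians and IQRs. Neither names a confidence bound to be compared with a margin.

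**The concern.** A study that reached significance, on the natural reading, found a difference or a change. Aim 2 has to rule out a deficit of more than some stated amount. The two tasks can need the same number of participants, but only if the deficit to be ruled out is as large as the difference the earlier studies were sized to find. The document gives neither quantity, so the rationale cannot be carried from one task to the other.

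What is at stake is the conclusion. With 60 described as sufficient, no margin, and an ANOVA as the planned comparison, a non-significant arm difference with a wide interval could be reported as showing the kiosk to be at least equivalent. The interval itself might still allow a sizeable deficit.

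**Working it through.** **Inputs from the document.** Required total 60; dropout 30%; minimum enrolment 78, requested 120 (all section 6.6.2); two arms (section 6.1). Not stated anywhere: margin, SD, alpha, power, expected difference, allocation ratio.

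**Assumptions.** 1:1 allocation, true difference zero, one-sided 2.5%, 80% power, no covariate adjustment unless noted. Results are in SD units; the ng/mL figures use assumed SDs of 6, 8 and 10.

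**1. The plan's own figures.** 60 cannot be reproduced, since no input to it is given. The 78 reproduces as 60 × 1.30 = 78. (Dividing by the retained fraction would give 60 / 0.70 = 85.7, so 86. That is a separate matter, and the requested 120 covers it.) After 30% loss, 120 leaves 120 × 0.70 = 84 and 78 leaves 78 × 0.70 = 54.6, about 55.

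**2. What 60 corresponds to.** By the normal approximation, the standardized difference matched to 30 per arm is (1.960 + 0.842) × √(2/30) = 2.802 × 0.2582 = 0.72 SD. The same expression serves for detecting a difference of that size (two-sided 5%) and for excluding a deficit of that size (one-sided 2.5%, true difference zero).

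**3. Precision.** The 95% CI half-width is t(0.975, 2n − 2) × √(2/n), with n per arm:
- 60 completers, n = 30: 2.002 × 0.2582 = 0.517 SD.
- 84 completers, n = 42: 1.989 × 0.2182 = 0.434 SD.

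**4. Smallest margin with 80% power.** Solve for m in P(T > t(0.975, 2n − 2)) = 0.80, where T is noncentral t with 2n − 2 degrees of freedom and noncentrality m / √(2/n):
- n = 30: m = 0.736 SD (0.851 SD for 90% power).
- n = 42: m = 0.619 SD.

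**5. Effect of baseline adjustment.** With baseline correlation r, the residual SD shrinks by √(1 − r²): 0.866 at r = 0.5 and 0.714 at r = 0.7 (assumed values). At 60 completers:
- Half-width: 0.517 × 0.866 = 0.45 SD and 0.517 × 0.714 = 0.37 SD.
- Margin for 80% power: 0.736 × 0.866 = 0.64 SD and 0.736 × 0.714 = 0.53 SD.

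| Case | 95% CI half-width | Margin for 80% power |
|---|---|---|
| 60 completers, unadjusted | 0.52 SD | 0.74 SD |
| 84 completers, unadjusted | 0.43 SD | 0.62 SD |
| 60 completers, adjusted, r = 0.5 | 0.45 SD | 0.64 SD |
| 60 completers, adjusted, r = 0.7 | 0.37 SD | 0.53 SD |

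**6. On the serum scale.** For 60 completers unadjusted and SDs of 6, 8 and 10 ng/mL, the half-width is 3.1, 4.1 and 5.2 ng/mL, and the margin for 80% power is 4.4, 5.9 and 7.4 ng/mL.

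**7. Dependence on the margin.** At 30 per arm, unadjusted, power is 21% for a margin of 0.3 SD, 48% for 0.5 SD and 97% for 1.0 SD. The same 60 is far too few or ample depending on a number the document does not contain.

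**The case against.** The strongest reply is that this is a pilot. The title calls it a pilot feasibility study, Aim 1 is acceptability and feasibility, section 6.6.1 calls the serum analyses exploratory, and section 6.6.2 offers pilot status as its reason. A formal non-inferiority calculation is not always expected of a pilot. That stands, and it is why the remedy is a precision statement and not a larger trial. It does not justify calling 60 required while Aim 2 sets out to demonstrate equivalence.

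It is also fair to say that up to 120 may be enrolled and that baseline adjustment is planned. Both improve precision, as the table shows, but neither supplies a margin. If only 78 are enrolled, about 55 remain, slightly worse than the 60-completer case.

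Four stronger readings are tempting, and the document does not support them.
- *That 60 is too small.* Without a margin this cannot be shown. For a margin of about 0.74 SD or more, 60 completers would do.
- *That a size for detecting a difference says nothing about excluding one.* Step 2 shows otherwise: with a true difference of zero, the size that detects a given difference also excludes a deficit of the same amount.
- *That the source studies were of similar size, or that choosing them for significance inflated the effect behind 60.* Their sizes and effects are not given, population and approach were also selection features, and no effect is visibly carried into 60. Even that they found a difference is an inference from the wording.
- *That about four times 60 is needed.* This presumes both that 60 was powered for some difference and that the margin is half of it. The document states neither.

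**Conclusion.** The point holds as a gap in justification. Nothing in section 6.6.2 supports 60 as adequate for Aim 2, because earlier significance is not a margin and the document has no margin, SD, alpha or power. Nor does anything show 60 to be inadequate.

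Its size, under the stated assumptions, is a smallest margin with 80% power of about 0.74 SD for 60 completers and 0.62 SD for 84, both unadjusted, or 0.64 to 0.53 SD for 60 completers if baseline correlates 0.5 to 0.7 with the week-10 value. The conversion to ng/mL depends wholly on the assumed SD. The practical risk is that a non-significant comparison is read as equivalence. This should be corrected; it does not call enrolment into question.

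**What to change.** Keep enrolment as it is.

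- In section 6.6.2, replace the significance-based rationale and the label calling 60 required with a precision statement. It should give the expected 95% CI half-width and the smallest margin with 80% power, for both 60 and 84 completers, with the assumptions on allocation, alpha, true difference and baseline correlation shown.
- In sections 6.1 and 6.6.1, report Aim 2 as the baseline-adjusted week-10 difference between arms with its 95% CI.
- State that a non-significant difference will not be taken as showing the kiosk at least equivalent. Non-inferiority may be claimed only if the CI excludes a margin that was justified before the data were seen. If no such margin was set, the result stands as an estimate.

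The cost is about one paragraph and no added participants. The downside is that the stated adequacy of the sample and the claim available under Aim 2 both become less favourable.

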6.6 Statistical Methods Planned in the Protocol and Determination of Sample Size

6.6.1 Statistical and Analytical Plans

The original analysis plan will be carried out using all available subject data points. No interim analysis will be performed. Exploratory data analyses will be conducted on the serum vitamin D levels of participants assigned to either the oral vitamin D supplementation or kiosk group. The analysis will be restricted to participants with valid baseline serum vitamin D data and at least one follow-up blood draw. The Shapiro-Wilk test will be used to assess the normality of the data distribution. Measures of central tendency and dispersion are provided for continuous data as medians (mdn) with associated interquartile ranges (IQR). Summary statistics will be provided for categorical variables and include the number of participants as well as the prevalence within each group.

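### The enrolment minimum of 78 adds 30% to 60 instead of dividing 60 by 0.70; at the plan's own dropout rate it leaves about 55 completers, and the minimum should be 86.

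*Combined protocol and SAP*

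**What the plan says.** The sample-size table in section 6.6.2 has three rows. The row "Estimate Required Sample Size" gives 60, the row "Estimate Participant Drop Out / Withdrawal" gives 30%, and the enrolment row reads "Minimum of 78, requesting 120". The text above the table says that approval was sought to "enroll twice the number required, or 120 subjects", to guard against high attrition or unusually strong interest in the study.

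The 60 is not derived from a stated calculation. The plan says that "the appropriate sample size was estimated based on previous and current studies that achieved significance" in this population with a similar approach.

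Two other sections bear on the point. Section 6.6.1 says the analysis will be "restricted to participants with valid baseline serum vitamin D data and at least one follow-up blood draw". Section 6.1 says that about 120 volunteers will be approached, and it describes block randomisation to two groups without giving the allocation ratio.

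**The concern.** The three table figures look like a chain: a required number, a loss rate, and an enrolment figure that allows for the loss. The last step appears to add 30% of the required number. But 30% of 60 is 18, while 30% of those enrolled is more than 18 once more than 60 are enrolled. The allowance is therefore smaller than the loss it is meant to cover.

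If recruitment stops at the stated minimum and dropout runs as estimated, the trial finishes below the size it calls required. For a study with a non-inferiority objective (sections 6.1 and 6.2), fewer participants means a less precise comparison of 25(OH)D between the groups, which makes non-inferiority harder to show. The study also tracks attrition in each arm as a feasibility result (section 6.5.1), so its own attrition allowance should be right.

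**Working it through.** **Inputs**, all from section 6.6.2:

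- required number n = 60
- dropout d = 0.30
- stated minimum = 78
- requested enrolment = 120

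**Reproducing the plan's figure.** n x (1 + d) = 60 x 1.30 = 78.0. This matches the stated minimum exactly.

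**The figure that meets the requirement.** With dropout d, the expected number remaining from N enrolled is N x (1 - d). Setting N x 0.70 >= 60 gives N >= 60 / 0.70 = 85.7, rounded up to 86. Working by arm, and assuming equal allocation, 30 / 0.70 = 42.9, rounded up to 43 per arm, which is again 86 in total. The gap is 86 - 78 = 8.

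**What each enrolment delivers:**

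| Enrolled | Expected completers at 30% dropout | Largest dropout that keeps 60 |
|---|---|---|
| 78 | 78 x 0.70 = 54.6 | 1 - 60/78 = 23.1% |
| 86 | 86 x 0.70 = 60.2 | 1 - 60/86 = 30.2% |
| 120 | 120 x 0.70 = 84.0 | 1 - 60/120 = 50.0% |

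**Shortfall at 78.** 60 - 54.6 = 5.4, and 5.4 / 60 = 9%.

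**Chance of reaching 60.** Assume each participant drops out independently with probability 0.30, so that completers follow a binomial distribution. The probability of at least 60 completers is then 11% with 78 enrolled, 57% with 86, and above 99.9% with 120. So 86 meets the requirement on average only; it does not guarantee it.

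**Effect on precision.** If the width of a confidence interval scales with 1/sqrt(N), going from 60 to 54.6 widens it by a factor of sqrt(60 / 54.6) = 1.048, about 5%.

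**Completers and the analysis set.** Section 6.6.1 counts anyone with a valid baseline and one follow-up draw. With 78 enrolled, a 30% dropout is 78 x 0.30 = 23.4 people, while 60 analysable participants allow only 78 - 60 = 18 to be lost. So 23.4 - 18 = 5.4 of the 23.4 dropouts, or 23%, would have to leave a usable follow-up draw before the shortfall disappeared.

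**The case against.** The strongest reply is that nobody plans to stop at 78. The same section requests 120, expressly to absorb attrition, and 120 keeps 60 participants at any dropout up to 50%. That is correct, and it limits the consequence. It does not rescue the 78, which is the only floor stated. Section 6.1 describes about 120 as the number to be approached, so enrolment of 120 is not assured.

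A second reply is that a dropout may still be analysable. This stands in part: someone lost between the 10-week and 14-week draws still counts under section 6.6.1. But no follow-up blood is drawn before the 10-week visit, so a participant who leaves during the intervention and has no later draw contributes nothing. The plan does not say when the 30% is expected to leave, so it gives no basis for assuming that the shortfall vanishes.

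Third, the text can be read as attaching the 30% to a worse-than-expected scenario, while the table lists it as the estimate. The table reading is used here because 78 is built from it. On either reading, 78 does not protect 60 against a 30% loss.

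Finally, the missing basis for the 60 is arguably the larger weakness. The plan defines no non-inferiority margin or precision target, so the harm cannot be expressed as lost power, and the roughly 5% widening is modest. Both points are fair. They limit what can be claimed about consequences but leave the arithmetic untouched.

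**Conclusion.** The concern holds. The stated minimum is 60 x 1.30, and it fails the plan's own dropout assumption: about 55 completers against 60 required, a 9% shortfall. The consistent minimum is 86.

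This rests on two readings: that 30% is the expected loss among those enrolled, as the table presents it, and that the 60 is meant as the number remaining after dropout, which is what a separate dropout row implies. The figure of 55 refers to completers; the analysable number would be somewhat higher if part of the loss comes after the 10-week draw.

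The figure should be corrected, but the practical effect is small: it bites only if enrolment ends below 86. The title page gives a study completion date of 11 March 2019, so the main remaining use of the correction may be to judge the achieved enrolment against the right target.

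**What to change.** In the enrolment row of the section 6.6.2 table, change the minimum from 78 to 86 and leave the requested 120 as it is. A short note showing 60 / 0.70 = 85.7, rounded up, would make the step checkable.

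If the sponsor prefers to keep 78, the table should say that about 55 completers are expected at 30% dropout, or that 78 supports 60 only up to 23% dropout. The second option is weaker, because 23% would then sit beside a 30% estimate and the difference would need explaining. In either case, one sentence should say whether 30% is the expected rate or a worst case, and whether it counts people lost after the 10-week draw.

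The cost is one table entry and a sentence of text. The design, arms and procedures do not change, and 86 lies within the 120 already requested. The documents do not say whether such a correction needs to go to the IRB, so that should be checked.
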